2	V 3.0	14/03/2017	[name]	
 - Revision of study procedures and outcome analysis for gr. 7 participant at M1D0 and M1D7
3	V 4.0	11/05/2017	[name]	
 - Revision to allow the use of screening lab tests for enrollment evaluation if interval between and screening and enrolment is three days or less.
4	V 5.0	2/11/2017	[name]	
 - Revision to allow additional PK assessments if additional data are required.

LIST OF ABBREVIATIONS:

AE	Adverse event
ALT	Alanine aminotransferase
anti-CS	Antibody to the P. falciparum circumsporozoite (CS) repeat domain
anti-HBs	Antibody to the hepatitis B surface antigen
AS01B	GSK's proprietary Adjuvant System containing MPL, QS-21 and liposome (50 µg MPL and 50 µg QS-21)
AS01E	GSK's proprietary Adjuvant System containing MPL, QS-21 and liposome (25 µg MPL and 25 µg QS-21)
AST	Aspartate aminotransferase
CI	Confidence interval
CREA	Creatinine
CRF	Case report form
CS	Circumsporozoite protein of P. falciparum
DHA-PIP	Dihydroartemisinin–piperaquine
DSMB	Data safety monitoring board
ECG	Electrocardiogram
ELISA	Enzyme linked immunosorbent assay
EPT	Endpoint titre
FDA	Food and Drug Administration, United States
GCP	Good clinical practice
GSK	GlaxoSmithKline
Hb	Haemoglobin
HBsAg	Hepatitis B surface antigen
HBV	Hepatitis B virus
HCV	Hepatitis C virus
Hep B	Hepatitis B
HIV	Human immunodeficiency virus
IB	Investigator's brochure
ICF	Informed consent form
ICH	International Committee on Harmonization
IEC	Independent ethics committee
IgG	Immunoglobulin G
IM	Intramuscular
IRB	Institutional review board

IU	International unit
kg	Kilogram
MedDRA	Medical Dictionary for Regulatory Activities
mg	Milligram
mL	Milliliter
ms	Millisecond
MPL®	3-deacylated monophosphoryl lipid A
MVI	Malaria Vaccine Initiative
P. falciparum	Plasmodium falciparum
PFS	Pre-filled syringe
PI	Principal Investigator
PLT	Platelets
PQ	Primaquine
QS-21	' Quillaja saponaria 21': a triterpene glycoside purified from the bark of the soap bark tree, Quillaja saponaria
RTS	Hybrid protein comprising HBs (hepatitis B surface antigen) and CSP portions
RTS,S	Particulate antigen, containing both RTS and HBs proteins
SAE	Serious adverse event
SLD-PQ	Single low dose Primaquine
SOP	Standard operating procedure
ULN	Upper limit of normal
WBC	White blood cells
WRAIR	Walter Reed Army Institute for Research

1 SYNOPSIS

Study Title	Safety and immunogenicity evaluation of the malaria vaccine, RTS,S/AS01, in healthy Thai adults
Study Design	Randomized, open label, single centre, Phase 2 study
Study Participants	
190 healthy non-pregnant Thai adults, aged 18-55 years, inclusive, will be recruited.
Study arms	
See Table 3 for dosing table
 
1. RTS,S/AS01B Fractional dose group (Group 1, n=20) will receive RTS,S/AS01B standard dose at Month 0 and Month 1 + RTS,S/AS01B fractional dose (1/5th dose) at Month 2.2. Double RTS,S/AS01E Fractional dose group (Group 2, n=20) will receive a double dose of RTS,S/AS01E standard dose at Month 0 and Month 1 + a double dose of RTS,S/AS01E fractional dose (1/5th dose) at Month 2.3. RTS,S/AS01E Standard dose group (Group 3, n=30) will receive RTS,S/AS01E standard dose at Month 0, Month 1 and Month 2.4. RTS,S/AS01E + DHA-PIP+PQ Standard dose group (Group 4, n=30) will receive RTS,S/AS01E standard dose + DHA-PIP+PQ at Month 0, Month 1 and Month 25. RTS,S/AS01E Fractional dose group (Group 5, n=30) will receive RTS,S/AS01E standard dose at Month 0 and Month 1 + RTS,S/AS01E fractional dose (1/5th dose) at Month 2.6. RTS,S/AS01E + DHA-PIP+PQ Fractional dose group (Group 6, n=30) will receive RTS,S/AS01E standard dose + DHA-PIP+PQ at Month 0 and Month 1 + RTS,S/AS01E fractional dose (1/5th dose) + DHA-PIP+PQ at Month 2.7. RTS,S/AS01E + DHA-PIP+PQ Fractional two-dose group (Group 7, n=30) will receive RTS,S/AS01E standard dose + DHA-PIP+PQ at Month 0 + RTS,S/AS01E fractional dose (1/5th dose) + DHA-PIP+PQ at Month 2.

	
Standard dose RTS,S/AS01B: 50µg RTS,S + standard dose AS01B (0.5ml containing 50µg MPL + 50µg QS21)
 
Standard dose RTS,S/AS01E: 25µg RTS,S + standard dose AS01E (0.5ml containing 25µg MPL + 25µg QS21)
 
Fractional dose RTS,S/AS01B (1/5th dose): 10µg RTS,S + 1/5 standard dose AS01B (0.1ml containing 10µg MPL + 10µg QS21)
 
Fractional dose RTS,S/AS01E (1/5th dose): 2.5µg RTS,S + 1/5 standard dose AS01E (0.1ml containing 2.5µg MPL + 2.5µg QS21)
 
DHA-PIP: Dihydroartemisinin–piperaquine co-formulated, given on day of vaccination (day 0) and each of the subsequent two days (days 1 and 2 post-vaccination).
 
PQ: Primaquine, given on day of vaccination (day 0).

Number of vaccine vials needed	
 • 60 vials RTS,S/AS01B (adult formulation) • 540 vials RTS,S/AS01E (standard formulation)
Planned Study Period	
6 months for each participant, from receipt of first vaccination
 
3 months to recruit 190 eligible volunteers
 
Total 9 months

Objectives	
 • 1) To assess the safety and immunogenicity of the standard formulation of the RTS,S vaccine (RTS,S/AS01E) in Thai adults. • 2) To assess the safety and immunogenicity of the adult formulation of the RTS,S vaccine (RTS,S/AS01B) in Thai adults. • 3) To compare the safety and immunogenicity of a fractional dose RTS,S regime (where the third dose is a 1/5th of the standard dose) using the adult formulation (RTS,S/AS01B) to the safety and immunogenicity of fractional dose RTS,S regimes using either single or double doses of the standard formulation (RTS,S/AS01E), in Thai adults. G1 vs G2 vs G5 • 4) To compare the safety and immunogenicity of fractional dose regime (where the third dose is a 1/5th of the standard dose) using a single dose of the standard formulation (RTS,S/AS01E) to the safety and immunogenicity of fractional

dose RTS,S regime using a double dose of the standard formulation (RTS,S/AS01E), in Thai adults. **G2 vs G 5**

- 5) To compare the **serologic response** to RTS,S/AS01E vaccine when co-administered with DHA-PIP + SLD-PQ with RTS,S/AS01E vaccine alone in adults, when RTS,S/AS01E is given in either a fractional dose regime (where the third dose is a 1/5th of the standard dose) or a full standard dose regime. **G2 vs G3 and G4 vs G6**
- 6) To compare the serologic response to RTS,S/AS01E vaccine co-administered with DHA-PIP + SLD-PQ, when RTS,S/AS01E is given in a fractional two-dose regimen (Month 0, standard dose and Month 2, fractional (1/5th) dose) with RTS,S/AS01E vaccine co-administered with DHA-PIP + SLD-PQ, when RTS,S/AS01E is given in a fractional three-dose regimen (Month 0 and Month 1, standard doses and Month 2, fractional (1/5th) dose) **G6 vs G7**

Primary Outcomes

- The safety of the investigational vaccine in each group:
 - Occurrence of serious adverse events (SAEs) from the date of the first vaccination to 29 days after the last vaccination, according to the MedRA classification.
 - Occurrence of SAEs during the whole study period, i.e. during a 6 month follow up period from the receipt of first vaccination, according to the MedRA classification.
- For groups 1 to 6, the concentration of antibodies against *Plasmodium falciparum* circumsporozoite (anti-CS antibody), one month after the first dose (at Study month 1), one month after the second dose (at Study month 2), one month after the third dose (at Study Month 3) and six months after the first dose (at Study Month 6).
- For group 7, the concentration of antibodies against *Plasmodium falciparum* circumsporozoite (anti-CS antibody), one month after the first dose (at Study month 1), two months after the first dose (at Study month 2), one month after the second dose (at Study month 3), and six months after the first dose (at Study Month 6).

Trial centre	Hospital for Tropical Disease Faculty of Tropical Medicine Mahidol University [name] [name] Thailand
Medical monitor	[name] (MORU)
DSMB (chair)	[name] (KEMRI/Kilifi Wellcome Trust)
Study monitor	[name] Mahidol-Oxford Tropical Medicine Research Unit (MORU) Faculty of Tropical Medicine Mahidol University [name] [name] Thailand

2 BACKGROUND AND RATIONALE

The malaria vaccine, RTS,S/AS01, consists of hepatitis B virus surface antigen virus-like particles incorporating a portion of the *Plasmodium falciparum*-derived circumsporozoite protein and a liposome-based adjuvant (AS01) containing two immune enhancers MPL (3'-O-desacyl-4'-monophosphoryl-lipid A) and QS-21 (*Quillaja saponaria* Molina, fraction 21)¹. In a large Phase 3 trial of RTS,S/AS01E at 11 sites in seven sub-Saharan African countries, efficacy against clinical malaria in children aged 5–17 months following three primary doses was 45.1% (CI 41.4 to 48.7), 35.2% (CI 30.5 to 39.5) and 28.3% (CI 23.3 to 32.9) during 20, 32 and 48 months of follow-up, respectively². In July 2015, RTS,S/AS01E received a positive scientific opinion by the European Medicines Agency for active immunization of children aged 6 weeks to 17 months against malaria³.

Other than considering RTS,S/AS01E for inclusion in the expanded programme of immunisations (EPI) in sub-Saharan Africa, the vaccine could be used as an innovative and potentially critical additional tool in the effort to stop the spread of artemisinin-resistant *falciparum* malaria in Southeast Asia. Multidrug-resistant *P. falciparum* strains have replaced the susceptible wild type in many parts of Cambodia⁴, where chloroquine, pyrimethamine, and sulphadoxine resistance originated, and from where these strains spread to Africa at a cost of millions of children's lives^{5, 6}. With the subsequent development of resistance to artemisinin combination therapy (ACT), the

usefulness of ACTs in Cambodia has been compromised⁷ and malaria incidence in northeast Cambodia is again on the rise. These resistant *P. falciparum* strains have spread across the Greater Mekong Subregion (GMS), compromising ACT efficacy, and they are now encroaching on the Indian subcontinent, the traditional gateway of malaria resistance to Africa⁸. There is a large and growing sub-Saharan African population that is immunologically naïve to malaria due to the dramatic reductions in malaria transmission during the last decade. If artemisinin-resistant *P. falciparum* strains are introduced and spread in sub-Saharan Africa, this could give rise to a surge in malaria-related illness and death, as was seen during the spread of chloroquine resistance in the 1980s and 1990s⁹. The only way to stop the spread of artemisinin-resistant malaria is through the elimination of *P. falciparum* in the GMS while this is still possible.

Targeted malaria elimination (TME), which comprises appropriate case management by village health workers, vector control and mass drug administration, is currently being implemented through pilot projects in selected villages in the Greater Mekong Subregion (GMS) and the scale-up of the intervention to the regional level are underway. TME is a time-consuming, demanding and difficult process requiring several months for regional coverage. Importantly, the elimination of individual *P. falciparum* parasitaemia using anti-malarial drugs is short-term; untreated parasitaemic travellers and migrants can readily re-introduce infections into treated villages. There is a concern that TME can achieve only a transient reduction in malaria followed by resurgence. Based on mathematical modelling, extending the post-TME parasitaemia-free period in the majority of villagers for as short as 200 days will substantially increase the chances of achieving the interruption of malaria transmission.

The mass administration of antimalarials like DHA/piperaquine can interrupt malaria transmission for limited time periods. To achieve longer lasting interruptions it would be critical to prevent re-infections, and the addition of mass vaccination campaigns integrated in mass drug administration campaigns may achieve this goal.

Immunogenicity of RTS,S is greater in older children, and the short term malaria protective effect is stronger than the overall effect assessed over 1-2 years. Addition of mass RTS,S/AS01E vaccination to the TME arsenal could provide this much needed additional protection.

Prior to the roll out of the combination of antimalarials with a vaccine it is mandatory to assess and confirm safety and vaccine immunogenicity.

RTS,S has not been used in combination with antimalarial drugs in the past. There is no practical or theoretical reason why the antimalarial drugs dihydroartemisinin/piperaquine and primaquine should

have any influence on the immunogenicity or safety of the RTS,S/AS01 vaccine. The only potential reason why there could be interference is the observation that the immunogenicity of live rabies vaccine is reduced by co-administration with chloroquine. The WHO therefore has warned that the concurrent use of chloroquine can reduce the antibody response to intradermal application of cell-culture rabies vaccines. People who are currently receiving malaria prophylaxis or who are unable to complete the entire three-dose rabies vaccine pre-exposure series before starting malarial prophylaxis should receive pre-exposure vaccination by the intramuscular route. In the past there have been no safety concerns regarding the co-administrations of vaccines with antimalarials.

Currently there are no safety and immunogenicity data for the use of RTS,S/AS01 in Asian populations. This trial will generate the required data for the use of this vaccine in Asian populations. For integration with the current TME activities, which provide mass drug administrations at months M0, M1, and M2, it would be most efficient and practical to provide the vaccine at the same intervals. To address a two round intervention (M0, M2) where a three round intervention is not feasible, one study arm will look at the immune response generated by only two doses of vaccine and antimalarial medications. Recent evidence suggests that a vaccination schedule which includes a fractional dose of RTS,S/AS01 (1/5th of the standard dose) could be similarly or more protective than a schedule with three standard doses, while requiring less vaccine and resources¹⁰. The evidence demonstrates that a change in immunization schedule that includes a dose reduction of the third RTS,S/AS01 vaccination, results in a significant increase in protection against controlled human malaria infection (CHMI) without an increase in the absolute antibody concentration after vaccination. Qualitative evaluation of immune responses showed that the third dose spacing and dose reduction increased somatic hypermutation in immunoglobulin genes and avidity. The trial therefore includes study arms which will assess the safety and immunogenicity of fractional dose schedules.

In summary: We propose to conduct a safety and immunogenicity trial of RTS,S/AS01 in Thai adults. The two major aims of this study are to 1) confirm that the co-administration of antimalarial drugs with the malaria vaccine RTS,S/AS01 does not reduce the immunogenicity of the vaccine, 2) assess the safety and immunogenicity of RTS,S/AS01 in Thai adults.

3 OBJECTIVES

The trial has the following objectives:

- To assess the safety and immunogenicity of the **standard formulation** of the RTS,S vaccine (RTS,S/AS01E) in Thai adults (Group 3 alone).
- To assess the safety and immunogenicity of the **adult** formulation of the RTS,S vaccine (RTS,S/AS01B) in Thai adults (Group 1 alone).
- To compare the safety and immunogenicity of a fractional dose RTS,S regime (where the third dose is a 1/5th of the standard dose) using the **adult formulation** (RTS,S/AS01B) to the safety and immunogenicity of fractional dose RTS,S regimes using either single or double doses of the standard formulation (RTS,S/AS01E), in Thai adults (Group 1 vs Group 2 and Group 1 vs Group 5).
- To compare the safety and immunogenicity of fractional dose regime (where the third dose is a 1/5th of the standard dose) using a single dose of the **standard formulation** (RTS,S/AS01E) to the safety and immunogenicity of fractional dose RTS,S regime using a double dose of the standard formulation (RTS,S/AS01E), in Thai adults (Group 2 vs Group 5).
- To compare the serologic response to RTS,S/AS01E vaccine when co-administered with DHA-PIP + SLD-PQ with RTS,S/AS01E vaccine alone in adults, when RTS,S/AS01E is given in either a fractional dose regime (where the third dose is a 1/5th of the standard dose) or a full standard dose regime (Group 3 vs. Group 4 and Group 5 vs Group 6).
- To compare the serologic response to RTS,S/AS01E vaccine co-administered with DHA-PIP + SLD-PQ, when RTS,S/AS01E is given in a fractional two-dose regimen (Month 0, standard dose and Month 2, fractional (1/5th) dose) with RTS,S/AS01E vaccine co-administered with DHA-PIP + SLD-PQ, when RTS,S/AS01E is given in a fractional three-dose regimen (Month 0 and Month 1, standard doses and Month 2, fractional (1/5th) dose) (Group 6 vs Group 7)

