4.2 Primary Outcome Measures

The primary outcome measures will be:

- The safety of the investigational vaccine in each group:
 - Occurrence of serious adverse events (SAEs) from the date of the first vaccination to 29 days after the last vaccination, according to the MedRA classification.
 - Occurrence of SAEs during the whole study period, i.e. during a 6 month follow up period from the receipt of first vaccination, according to the MedRA classification.

- For groups 1 to 6, the concentration of antibodies against *Plasmodium falciparum* circumsporozoite (anti-CS antibody), one month after the first dose (at Study month 1), one month after the second dose (at Study month 2), one month after the third dose (at Study Month 3) and six months after the first dose (at Study Month 6).
- For group 7, the concentration of antibodies against *Plasmodium falciparum* circumsporozoite (anti-CS antibody), one month after the first dose (at Study month 1), two months after the first dose (at Study month 2), one month after the second dose (at Study month 3), and six months after the first dose (at Study Month 6).

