8.2 The Number of Participants

The sample size calculations are based on the objective of comparing the serologic response to RTS,S/AS01E vaccine co-administered with DHA-PIP + SLD-PQ with RTS,S/AS01E or RTS,S/AS01B vaccine alone in adults. This is a phase II trial. Sample sizes for phase II trials are usually small, as safety is still of paramount importance. Valid sample sizes for comparing sample sizes between two groups are usually obtained using exact test methods such as the Fisher's exact test power calculations. This is done using simulations as sample size formulas are not well developed. To estimate the sample size we use a four-fold increase in anti-CS antibody titre as an assumed correlate of protection. For the sample size calculation, we assume that the background rate of response in the reference groups will be 5% and the true rate of anti-CS antibody response in the vaccine groups is 80%. We wish to exclude, for the vaccine, a one-tailed lower 95% CI for the reference-vaccine group difference of lower than 30%. The study aims to detect this difference with 90% power (because the detectable difference is big) and testing at 5% significance level. With these assumptions, and using the method of Blackwelder[37] for precision-based sample size calculations, a total of 20 participants per group would be needed for arms 1 and 2 because the anticipated difference is too big. However, for arms 3 to 7 (Table 3 below), we will need more participants per group because a smaller detectable effect is anticipated. Using the Fisher's exact test power simulations, a difference in serologic response of 30% (say 65% vs 95%) gives approximately 80% power with a sample size of 30 participants in each group testing at 5% significance level. Therefore the total sample size for all the 7 arms will be 190 participants.

The size of study groups is relatively small hence it is imperative to minimise potential losses. Whenever possible an attempt will be made to replace study participants should a participant be withdrawn or choose to withdraw. The stata command for obtaining the Fishers exact test power simulations is: `power two proportions 0.65 0.95, test(fisher) n1(30) n2(30)`. This has been performed in Stata 14.

The required sample sizes are summarized as follows:

Table 3: Sample size and vaccine vials required for each arm

Group	# participants	Vaccine	Dose M0	Dose M1	Dose M2	Antimalarial	vaccine vials required

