15 APPENDIX A: SUMMARY OF STUDY ARMS AND PROCEDURES

Month	Group 1 (n=20) $R_B R_B r_B$	Group 2 (n=20) $2xR_E 2xR_E 2xr_E$	Group 3 (n=30) $R_E R_E R_E$	Group 4 (n=30) $R_E R_E R_E + \text{DHA-PIP} + \text{PQ}$	Group 5 (n=30) $R_E R_E r_E$	Group 6 (n=30) $R_E R_E r_E + \text{DHA-PIP} + \text{PQ}$	Group 7 (n=30) $R_E r_E + \text{DHA-PIP} + \text{PQ}$
0	RTS,S/AS01B Standard dose (0.5mL)	RTS,S/AS01E Double Standard dose (1.0mL)	RTS,S/AS01E Standard dose (0.5mL)	RTS,S/AS01E Standard dose (0.5mL) + DHA-PIP+PQ	RTS,S/AS01E Standard dose (0.5mL)	RTS,S/AS01E Standard dose (0.5mL) + DHA-PIP+PQ	RTS,S/AS01E Standard dose (0.5mL) + DHA-PIP+PQ
1	RTS,S/AS01B Standard dose (0.5mL)	RTS,S/AS01E Double Standard dose (1.0mL)	RTS,S/AS01E Standard dose (0.5mL)	RTS,S/AS01E Standard dose (0.5mL) + DHA-PIP+PQ	RTS,S/AS01E Standard dose (0.5mL)	RTS,S/AS01E Standard dose (0.5mL) + DHA-PIP+PQ	No intervention in M1
2	RTS,S/AS01B 1/5 Standard dose (0.1mL)	RTS,S/AS01E Double 1/5 Standard dose (0.2mL)	RTS,S/AS01E Standard dose (0.5mL)	RTS,S/AS01E Standard dose (0.5mL) + DHA-PIP+PQ	RTS,S/AS01E 1/5 Standard dose (0.1mL)	RTS,S/AS01E 1/5 Standard dose (0.1mL) + DHA-PIP+PQ	RTS,S/AS01E 1/5 Standard dose (0.1mL) + DHA-PIP+PQ

R_B = Standard dose RTS,S/AS01B: 50µg RTS,S + standard dose AS01B (0.5ml containing 50µg MPL + 50µg QS21)

R_E = Standard dose RTS,S/AS01E: 25µg RTS,S + standard dose AS01E (0.5ml containing 25µg MPL + 25µg QS21)

r_B = Fractional dose RTS,S/AS01B (1/5th dose): 10µg RTS,S + 1/5 standard dose AS01B (0.1ml containing 10µg MPL + 10µg QS21)

r_E = Fractional dose RTS,S/AS01E (1/5th dose): 2.5µg RTS,S + 1/5 standard dose AS01E (0.1ml containing 2.5µg MPL + 2.5µg QS21)

2x = Double dose of R_E (i.e. 1.0ml) or r_E (i.e. 0.2ml), as indicated.

DHA-PIP = Dihydroartemisinin/piperazine (for 3 days; day of vaccination and two subsequent days)

PQ = Primaquine (single low dose on day of vaccination)

Study procedures

Month	Scr	M0				M1				M2				M3	M6 ^a	
Day of month		0 ^f	1 ^b	2 ^b	7	0	1 ^b	2 ^b	7	0	1 ^b	2 ^b	7	0	0	
Informed Consent	x															
Inclusion / Exclusion criteria	x	x														
Vaccination		x				x*				x						
DHA/piperazine**		x	x ^b	x ^b		x*	x ^b	x ^b		x	x ^b	x ^b				
PQ single low dose primaquine**		x				x*				x						
History of fever, current axillary temperature***	x	x	x ^b	x ^b	x	x	x ^b	x ^b	x	x	x ^b	x ^b	x	x	x	
Full medical history, vital signs, physical examination	x	x				x				x						

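### Objective 1 and the antimalarial comparison are tied to single arms of 30 with no distinction by time point, although identically treated arms could be pooled at Months 1 and 2

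*Protocol*

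**What the plan says.** Section 3 (Objectives) names the groups for each objective. Safety and immunogenicity of the standard formulation are to be assessed in one arm: "RTS,S vaccine (RTS,S/AS01E) in Thai adults (Group 3 alone". The effect of co-administered antimalarials is to be assessed as "Group 3 vs. Group 4 and Group 5 vs Group 6". Neither statement refers to time points.

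Section 4.2 makes anti-CS antibody a primary outcome at four visits. For Groups 1 to 6 the first two are "one month after the first dose (at Study month 1), one month after the second dose (at Study month 2"). Months 3 and 6 follow.

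Table 3 (Section 8.2) and Appendix A give the regimens. Groups 3 and 5 both receive 0.5 mL RTS,S/AS01E at Months 0 and 1 without drug, and first differ at the Month 2 dose. Groups 4 and 6 follow the same pattern with DHA-PIP and primaquine. Group 7 has the same Month 0 round as Groups 4 and 6, and its Month 1 entry is "No intervention in M1".

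Section 8.2 sizes arms 3 to 7 for one pair: "say 65% vs 95%) gives approximately 80% power with a sample size of 30 participants in each group". Section 8.6 lists summaries for each study group. Section 8.4 limits the per-protocol set to participants who received three full, correct doses. The synopsis gives Objective 1 no group restriction and lists other pairs for the antimalarial objective: "G2 vs G3 and G4 vs G6".

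**The concern.** The closing summary of Section 2 puts first, of its two major aims, confirming that antimalarials do not reduce the vaccine's immunogenicity. At Months 1 and 2 the arms named in Section 3 are duplicates of one another. All seven arms come from one concurrent block randomisation (Section 4.8.4), so combining duplicates keeps the comparison randomised.

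By naming fixed groups regardless of time point, Section 3 has three consequences at these visits:
- The description of the vaccine alone uses one of two identical arms.
- The drug effect is reported as two separate 30 v 30 results that can differ by chance alone, with nothing in the treatment received so far to explain a difference.
- Group 7's Month 1 sample plays no part in the drug comparison.

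The stake is precision on the lead question, and on the standard formulation in a population for which Section 2 says no data exist.

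**Working it through.** **Inputs.** Arms of 30 (Table 3); regimens by month (Appendix A); primary antibody visits at Months 1, 2, 3 and 6 (Section 4.2); 65% v 95%, Fisher's exact test, 5% level, 30 per arm (Section 8.2, command "0.65 0.95, test(fisher) n1(30) n2(30"); 80% assumed response in vaccinated groups (Section 8.2).

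**1. The protocol's own figure.** Enumerating both binomials exactly, two-sided Fisher power for 65% v 95% at 30 v 30 is 78.8%, in line with the stated 80% or so. A one-sided test would give 86.7%. The stated figure stands.

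**2. Identically treated participants at each visit.**

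| Visit | Vaccine alone | Vaccine + drugs |
|---|---|---|
| Month 1 | 3+5 = 60 | 4+6+7 = 90 |
| Month 2, before the dose | 3+5 = 60 | 4+6 = 60 |
| Months 3 and 6 | regimens differ | regimens differ |

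The Month 2 sample qualifies because Section 4.2 defines it as "one month after the second dose (at Study month 2"), that is, as the response to the first two doses.

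**3. What Section 3 uses.** Objective 1 uses 30 of 60 at Months 1 and 2. For the antimalarial objective, the two pairs together use 120 of 120 at Month 2 and 120 of 150 at Month 1, so only Group 7 (30/150 = 20%) is left out.

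**4. Precision of the drug contrast.** The standard error of a mean difference is proportional to √(1/n₁ + 1/n₂).
- 30 v 30: √(2/30) = 0.258
- 60 v 60: √(2/60) = 0.183; ratio 0.183/0.258 = 0.71
- 60 v 90: √(1/60 + 1/90) = 0.167; ratio 0.167/0.258 = 0.65

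The fair benchmark is also the average of the two pairs. Its variance factor is (2/30)/2 = 0.0333, the same as 60 v 60. Against that average, Month 2 pooling gives one result instead of two but no new data. At Month 1, Group 7 lowers the factor to 0.0278, a standard error ratio of √(0.0278/0.0333) = 0.91.

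**5. On the protocol's scale.** With two-sided Fisher at 5%, power for 65% v 95% is 78.8% (30 v 30), 98.9% (60 v 60) and 99.8% (60 v 90). The drop from 95% detectable with 80% power is 30.5, 18.7 and 16.2 points.

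**6. On the titre scale.** The protocol gives no standard deviation. Assuming 0.3 to 0.6 on log10 titre, the 95% interval for a geometric mean ratio extends by a factor 10^(1.96 × SD × √(1/n₁ + 1/n₂)) either side:
- 30 v 30: 1.42 to 2.01
- 60 v 60: 1.28 to 1.64
- 60 v 90: 1.25 to 1.57

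**7. Objective 1.** For an 80% response the exact 95% interval is 61% to 92% with n = 30 (24/30) and 68% to 89% with n = 60 (48/60). With no events after a given dose, the two-sided exact upper limit 1 − 0.025^(1/n) is 11.6% with n = 30 and 6.0% with n = 60.

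**The case against.** The strongest reply is that the antimalarial objective is regimen-specific: it asks about co-administration within a standard or a fractional schedule, and a schedule is complete only after the Month 2 dose. Group 3 is likewise the only arm that receives three standard RTS,S/AS01E doses without drug. Both points stand. At Months 3 and 6 the present groups are right and nothing should change. The two primary SAE outcomes run past the Month 2 dose, so they cannot be pooled either.

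A second reply is that combining arms belongs in the statistical analysis plan, which is not shown. This stands in part. Section 3 lists pairs without time points and Section 8.6 does not forbid a combined estimate. But the restriction of Objective 1 to Group 3 is stated, so a plan that pooled would depart from it. For the drug effect, the groups named in the objective are the ones a plan would carry forward.

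Three stronger readings are tempting, and the document does not support them:
- A reader might infer that half or more of the randomised data goes unused. That is true of Objective 1 at Months 1 and 2, and of any one pair. It is not true of the antimalarial objective, where both pairs are analysed.
- A reader might infer that the pairs are prescribed at every time point. Section 3 is silent on this.
- A reader might infer that the comparisons are underpowered or the power figure wrong. The 80% reproduces for the difference stated.

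Power to detect a difference is also a poor measure of an aim to confirm no reduction. The standard errors and interval widths are the better guide.

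**Conclusion.** The point holds as a loss of efficiency at Months 1 and 2. Objective 1 uses 30 of 60 identically treated participants. The drug effect is reported in two halves where one comparison is available, with a standard error 0.71 (Month 2) or 0.65 (Month 1) times that of a single pair. Measured against both pairs averaged, the gain is one clear result at Month 2 and a ratio of 0.91 at Month 1. No stated figure is wrong, and the document does not support a claim that most of the data is discarded or that the pairs lack their stated power.

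The conclusion assumes that pooled arms do not differ in conduct or drop-out before their regimens diverge. Concurrent randomisation makes this reasonable, although the trial is open-label. The titre figures rest on an assumed standard deviation. The power figures rest on the protocol's 65% and 95%.

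**What to change.** In Sections 3 and 8.6, and in the synopsis objectives, define groups by the treatment received up to the time point.

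- **Co-administration:** compare 3+5 v 4+6+7 at Month 1 and 3+5 v 4+6 at Month 2. Keep 3 v 4 and 5 v 6 at Months 3 and 6.
- **Objective 1:** use Groups 3+5 for antibody at Months 1 and 2 and for per-dose safety summaries after doses 1 and 2. Use Group 3 alone from the Month 2 dose onward and for the cumulative SAE outcomes. The 30-day window in Section 6.21 can run past a 28-day interval, so count only events before the Month 2 dose in pooled summaries after dose 2.
- **Per-protocol set (Section 8.4):** replace the three-dose requirement with the doses scheduled for the arm up to the time point. Read literally, the present rule excludes all of Group 7, which is scheduled for two doses.
- **Synopsis:** bring its antimalarial pairs into line with Section 3. In the pairs it lists, both arms receive antimalarials or neither does, so they cannot show the drug effect.

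The cost is wording in four places and minor extra analysis. No participants, visits or samples are added, and the sample size statement can stay as it is.
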